The study is a parallel, single-blind, controlled, superiority trial in which participants will be randomized to a restrictive or a liberal transfusion group. This study will randomize 1520 Veterans at 15 VA Medical Centers. The total recruitment period will be approximately 4 years which will be followed by a 3 month active and 9 month passive follow-up period. The duration of the study will be approximately 5 years. Consent for the study will be obtained prior to the index surgical intervention at the clinic visit or, in case of inpatients, at the hospital ward pre- or postoperatively. Randomization will be performed via a central telephone randomization system once the participant has a confirmed Hb < 10gm/dl. Active follow up will be up to three months

after randomization. Passive follow up will be from 3 months to one year after randomization. The study flow is shown in FIGURE 3. There will be no blinding at the treating physician level; however the participants and the Endpoint Committee will be unaware of group allocation.

Follow up forms will be filled out during two postoperative clinic visits that will be after the 30th and 90th post-randomization days. Participants who cannot make the clinic visits will be assessed by phone call follow-up, during which they will be asked specific questions to ascertain whether signs or symptoms related to any of the endpoints have developed. In addition, the electronic medical record, will be assessed to collect relevant information. If a participant gets re-admitted at any time after discharge and within 90 days after randomization, the electronic medical record will be examined for the presence of any of the diagnoses that consist part of either the primary or any other endpoints. If the participant has been admitted to a non-VA facility, a full copy of hospital records from that admission will be obtained and assessed for the presence of any of the outcomes. History and physical, consultation notes and progress notes will all be reviewed. Furthermore, particular attention will be paid to laboratory reports for troponin, creatinine, CK-MB (if available), and WBC levels, reports of cardiac echograms, radiology reports, and results of cultures (blood, wound, sputum). Participant agreement for release of information to the study personnel for all postoperative hospital visits that occur within 90 days after randomization will be obtained as part of the original consent form.

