Clinical Data: The site coordinator will also collect clinical data using information from the medical record and consult with the surgeon as needed. These will include height, weight, last preoperative serum Hb, albumin, blood pressure, and history of comorbidities, including coronary artery disease, end-stage renal disease, chronic obstructive pulmonary disease, hyperlipidemia, diabetes mellitus, and hypertension.

To assure that MI or acute renal failure have not occurred prior to the time of randomization the patient's chart will be reviewed for Troponin, EKG, and serum creatinine. If these values are available in the 24 hrs. prior to randomization, they will not be collected again. If unavailable within this period, EKG, serum creatinine, and troponin data will be collected within 24 hours from the time of randomization. If available at the institution, CK-MB will also be collected (not required).

We will also collect information on prior history of MI, coronary artery bypass, and stent placement. Furthermore, intraoperative assessments will be collected during the surgical procedure, such as type of operation, amount of intraoperative blood loss, intraoperative transfusion, amount and type of fluids administered, and length of the operation.

Lab, transfusion, EKG ordering procedures: Once the participant is randomized, a study team member should enter a CPRS note indicating (1) randomization arm, (2) lab/EKG collection schedule, and (3) transfusion regimen. When possible, the lab, EKG, and transfusion orders should be placed by a study team member. If verbal lab or transfusion orders are given by the

LSI to a resident or nurse, the order should be co-signed by the LSI according to the local facility's standard operating procedure. If the co-sign option is unavailable under Orders, the LSI or study team member must enter a CPRS note after the order has been placed indicating that the order was placed by resident/nurse at the LSI's request. If the note is entered by a study team member, the note must be co-signed by the LSI.

2. Follow-up Assessment

Follow-up assessments will be collected after participants are discharged from the hospital including 30- day and 90-day active follow-up assessments and one-year passive follow-up assessment.

a) Thirty Day Follow-up

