The active follow up period for study purposes will be up to 90 days after randomization. If the participant refuses to continue participation during active follow up, his or her participation in the study will be terminated. All participants who complete the active follow-up phase of the study will be followed up to one year by the Chair's Office to assess mortality using a combination of phone call follow-up, search of the DAF, or electronic medical record

assessment. If a participant declines to participate in long term follow up then one year mortality data for this participant will not be collected. Given that the one year follow up is passive and does not involve any participant action we do not anticipate this to become a major issue.

X. TRANSFUSION STRATEGIES

Participants will be randomized to a liberal (transfuse if Hb <10 gm/dl) or restrictive (transfuse if Hb <7gm/dl) transfusion groups. Transfusion will be administered in order to maintain Hb just above the aforementioned thresholds for the index hospital stay or up to 30 days after randomization, whatever comes first. A participant must be randomized within 24-hrs of the first postoperative Hb falling below 10 gm/dl. It is strongly recommended that the transfusion treatment is initiated as soon as possible after and no longer than 24 hours from identifying a protocol-required transfusion Hb threshold. Transfusions will be administered according to the following scheme.

- A. Liberal group (transfusion trigger: Hb < 10 gm/dl)
 - i. If Hb < 7.5 gm/dl transfuse three units PRBCs, then check Hb. Based on the return Hb value, follow the transfusion protocol (steps i, ii, or iii) until Hb \geq 10.
 - ii. If $7.5 \leq$ Hb < 8.5 gm/dl transfuse two units PRBCs, then check Hb. Based on the return Hb value, follow the transfusion protocol (steps i, ii, or iii) until Hb \geq 10.
 - iii. If Hb \geq 8.5 gm/dl transfuse one unit PRBCs, then check Hb. Based on the return Hb value, follow the transfusion protocol (steps i, ii, or iii) until Hb \geq 10.
- B. Restrictive group (transfusion trigger: Hb < 7 gm/dl)
 - i. If Hb < 5.5 gm/dl transfuse of two units PRBCs, then check Hb. Based on the return Hb value, follow the transfusion protocol (steps i, or ii) until Hb \geq 7.
 - ii. If $5.5 \leq$ Hb < 7 gm/dl transfuse one unit PRBCs, then check Hb. Based on the return Hb value, follow the transfusion protocol (steps i, or ii) until Hb \geq 7.

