Participant Hb, creatinine, and troponin levels will be collected on days 1, 2, 3, 4, and 7 post-randomization or discharge (whatever is shortest). EKG will be performed on days 1 and 4 after randomization. If a participant is discharged prior to post-randomization day 4, EKG will be obtained at discharge. Results on Hb (standard of care/per transfusion protocol requirements), creatinine, troponin, and EKG performed at other time points will also be collected until discharge as supporting documentation for endpoint adjudication. If available at the institution, CK-MB will also be collected (not required).

Urine output will also be monitored in patients admitted to the Intensive Care Unit and it will be reviewed daily by the Study Coordinator. If the patient has anuria for more than 12 hours, or has urine output less than 0.3 ml/Kg/hr for more than 24 hours then the urine output will be documented as evidence for the development of ARF.

Hemoglobin and transfusion record: We will record the number of blood transfusions during the preoperative, intraoperative, and postoperative time periods. The protocol requires that Hb levels be measured on day of randomization, days 1,2,3, and 4 after randomization as well as on day 7 if the participant remains in the hospital. Hb measurements, performed as standard clinical practice, will also be recorded. The Site Coordinator will record information on a) preoperative, intra-operative, and postoperative transfusions, and b) Pre- and post-randomization Hb levels. Information on Hb levels and transfusions will be obtained by contacting the hospital laboratory directly or from the chart. Information on transfusions will be obtained from the chart and the blood bank.

XI. MONITORING AND REPORTING SERIOUS ADVERSE EVENTS

A. Importance of Serious Adverse Event Reporting

Timely and complete reporting of safety information assists study management in identifying any untoward medical occurrence, thereby allowing: a) protection of safety of study participants, b) a greater understanding of the overall safety profile of the study treatments and therapeutic modalities, c) improvements in study design or procedures, and d) compliance with regulatory requirements.

B. Role of the Local Site Investigator in Serious Adverse Event Monitoring

The local site investigator, as well as other site personnel, shall be personally responsible for the following requirements:

1. Closely monitoring all study participants for new SAEs;

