4. STUDY METHODS

4.1. General Study Design

The study is a parallel, single-blind, controlled, superiority trial in which participants will be randomized to a restrictive or a liberal transfusion group. This study will randomize 1520 Veterans at 15 VA Medical Centers. The total recruitment period will be approximately 4 years which will be followed by a 3 month active and 9 month passive follow-up period. The duration of the study will be approximately 5 years. Consent for the study will be obtained prior to the index surgical intervention at the clinic visit or, in case of inpatients, at the hospital ward pre- or postoperatively. Randomization will be performed via a central telephone randomization system once the participant has a confirmed post-operative Hb < 10gm/dl. Active follow up will be up to three months after randomization. Passive follow up will be from 3 months to one year after randomization. The study flow is shown in Appendix 1. There will be no blinding at the treating physician level; however the participants and the Endpoint Committee will be unaware of group allocation.

Follow up forms will be filled out during two postoperative clinic visits that will be after the 30th and 90th post-randomization days. Participants who cannot make the clinic visits will be assessed by phone call follow-up, during which they will be asked specific questions to ascertain whether signs or symptoms related to any of the endpoints have developed. In

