4.3. Randomization and Blinding

The clinical site coordinator will track the participants' postoperative Hb levels and identify participants whose Hb level is below 10 gm/dl and therefore eligible for randomization. iStat hemoglobin values may not be used as the basis for randomization/transfusion decisions. The CSPCC staff will prepare randomization schedules for each clinical site participating in the study. The study randomization to either liberal or restrictive transfusion policy will be done by an Interactive Touchtone Telephone Randomization System (ITTRS). A stratified block randomization scheme with block sizes of 2 and 4 will be used to randomize participants in the two transfusion groups. The stratifying factors are clinical site and revised cardiac risk index

(RCRI) class. The participants and the Endpoint Committee will be unaware of treatment group allocation.

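### The Endpoint Committee is declared blind, but the protocol lists post-randomization Hb as adjudication documentation and neither document says it is masked

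*Protocol*

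**What the plan says.** **The blind.** Protocol VI leaves treating physicians unblinded; "however the participants and the Endpoint Committee will be unaware of group allocation". SAP 4.1 repeats this, and SAP 4.3 (Randomization and Blinding) states: "The participants and the Endpoint Committee will be unaware of treatment group allocation". None of the three places gives a procedure.

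**The data flow.** Protocol X first sets the schedule: "Participant Hb, creatinine, and troponin levels will be collected on days 1, 2, 3, 4, and 7 post-randomization or discharge". The next relevant sentence covers unscheduled results: "Results on Hb (standard of care/per transfusion protocol requirements), creatinine, troponin, and EKG performed at other time points will also be collected". It then gives their purpose: they "will also be collected until discharge as supporting documentation for endpoint adjudication".

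**What the arms control.** Also in Protocol X: "Transfusion will be administered in order to maintain Hb just above the aforementioned thresholds". Those thresholds are 10 gm/dl (liberal) and 7 gm/dl (restrictive).

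**The committee.** Protocol XVII.B gives its composition and task. SAP 7.1 says that a clinical events committee adjudicates every component of the primary endpoint. Neither describes what adjudicators receive or what is removed first.

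**The chart and forms.** Under Protocol IX.C, after randomization "a study team member should enter a CPRS note indicating (1) randomization arm, (2) lab/EKG collection schedule, and (3) transfusion regimen". SAP Appendix 2 records Hb on Form 3 and transfusions on Form 4, apart from laboratory markers (Form 6) and MI confirmation (Form 8). Table 7 in SAP Appendix 5 reflects the same split between Forms 3 and 6.

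**The concern.** With an unblinded treating team, blinded adjudication is the main safeguard for components that need judgement. Here the protocol names, as adjudication material, the one laboratory value that the intervention is designed to separate. The liberal scheme repeats until Hb reaches at least 10 gm/dl, so a series that stays between 7 and 9 without correction points to the restrictive arm.

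The inference is imperfect. Hb can recover unaided, either arm may be transfused for rapid bleeding, and after an MI the investigator may depart from the assignment. A single low value says little, because the liberal scheme itself provides for Hb below 7.5 gm/dl.

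The component most exposed is MI. Death, coronary revascularization, creatinine-based renal failure and imaging-confirmed stroke leave less to judgement. The common in-hospital schedule of troponin, creatinine and EKG also limits unequal testing. If adjudicators could often guess the arm, borderline MI calls could shift in one arm, and that would affect both the type I error and the power of the primary test.

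**Working it through.** **1. The plan's own figure.** Protocol XVI.B assumes 30% (restrictive) v 22.5% (liberal), two-sided 5%, 90% power. With pooled variance and no continuity correction, p̄ = 0.2625 and

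n per arm = [1.96·√(2·0.2625·0.7375) + 1.2816·√(0.3·0.7 + 0.225·0.775)]² / 0.075² = 721.2, rounded up to 722.

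The total is 1444, as stated, and 1444/0.95 = 1520. Power at 722 per arm is 90.0%.

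**2. How many patients could turn on an MI call.** Protocol Table 2, stratum 6-9 gm/dl: composite 29.5%, death 15.3%, MI 11.0%, acute renal failure 11.1%, revascularization 0.4%. The non-MI components can cover at most 15.3 + 11.1 + 0.4 = 26.8%. MI is therefore the only component in at least 29.5 - 26.8 = 2.7% of patients.

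**3. Size of the shift (assumed).** Suppose 10-20% of those MI-only calls change in one arm. The documents give no figure for this. The shift b is 2.7% × 10% = 0.27 points or 2.7% × 20% = 0.54 points, about 2 to 4 of 722 patients.

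**4. Type I error.** True rate p = 30% in both arms, one arm recorded as p + b:

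SE0 = √(2·p̄(1-p̄)/722); SE1 = √{[(p+b)(1-p-b) + p(1-p)]/722}

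Rejection rate = Φ((b - 1.96·SE0)/SE1) + Φ((-b - 1.96·SE0)/SE1)

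For b = 0.0054 both standard errors are 0.02418, giving Φ(-1.737) + Φ(-2.183) = 0.0412 + 0.0145 = 5.57%. For b = 0.0027 the result is 5.14%. Removing calls instead of adding them gives 5.14% and 5.58%.

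**5. Power at the planned 30% v 22.5%.** The same formula, with the shift taken from one arm:

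| Shift b (points) | Restrictive arm loses the calls | Liberal arm loses the calls |
|---|---|---|
| 0 | 90.0% | 90.0% |
| 0.27 | 87.9% | 92.0% |
| 0.54 | 85.5% | 93.7% |

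The same b is used for both arms for simplicity. Table 2's rates are only a guide: they rest on a troponin I cutoff of 1 ng/ml on clinician-ordered tests, whereas the trial uses the Third Universal Definition with scheduled troponin.

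**The case against.** **Collected does not mean shown.** The sentence in Protocol X governs what is collected. It does not say that the committee sees unredacted Hb. A reader might infer that the committee is in fact unblinded, or that a manual withholding Hb would contradict the protocol. Neither follows: a procedure that collects Hb and then redacts it or releases it in stages would comply. The separate forms make such a procedure practicable, although they do not show that it exists. This objection stands and sets the strength of the conclusion.

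**Scope.** The adjudication clause attaches to results at other time points, not expressly to the scheduled Hb. That is also correct. The remedy should cover both because either series is informative, but the extension is ours.

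**The note naming the arm.** No text says that adjudicators receive the chart. The same holds for the Form 8 item on stopping or continuing the transfusion protocol after MI (SAP Appendix 5, Table 8), which does not name the arm. Both are items to exclude from packets, not evidence of a leak.

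**Hb may be needed.** The MI criteria are in Appendix I, which is not in the supplied text, and Protocol I describes coronary events as an imbalance of oxygen supply and demand. Hb may be a deliberate input. This stands, and it is a reason to offer staged release.

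**Larger effects.** A reader might treat all MI (11.0%) as MI-only and obtain a type I error up to 14.7% and power down to 64%. That requires that no MI patient also died, had renal failure or was revascularized. The components sum to 15.3 + 11.0 + 11.1 + 0.4 = 37.8% against a composite of 29.5%, so there is 8.3 points of overlap, and Table 2 does not show that MI has no part in it. The true MI-only share may exceed 2.7%, but the documents do not give it.

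**Conclusion.** The point holds as an avoidable risk: a stated data flow works against a stated safeguard, and neither document says how the two are reconciled. It should be fixed, because the remedy is simple and a claim of blinded adjudication cannot be verified from these documents as they stand.

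At the lower bound the numerical effect is small: type I error of 5.1-5.6%, and power between about 86% and 94% depending on the arm affected. This rests on the assumed 10-20% swing, on Table 2's MI-only minimum, and on Table 2's MI definition carrying over to the trial. The case rests on the text; the figures only show the scale.

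**What to change.** 1. **Protocol X.** Remove Hb from the adjudication documentation. Alternatively, state that any post-randomization Hb, scheduled or not, is released only after the blinded call is recorded, with later changes logged. Use staged release if the MI criteria in Appendix I need Hb.
2. **Protocol VI and SAP 7.1.** State that packets are built from troponin, creatinine, CK-MB where available, EKG, ICU urine output and other event records. Hb (Form 3), transfusion records (Form 4), the Form 8 transfusion item and any note naming the arm are withheld or redacted.
3. **SAP 7.1.** Confirm that the clinical events committee is the blinded Endpoint Committee of SAP 4.3.
4. **Events already adjudicated.** Document what was supplied. The protocol is at version 11, dated 12/18/2024, so some calls may exist. New wording cannot re-blind them, and re-adjudication is not requested.

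**Cost.** A few sentences in each document and redaction when packets are assembled, with more work if narrative notes are supplied. N, alpha and the number of assessors do not change. If earlier packets contained Hb, adjudication conditions would differ before and after the change, and this should be reported.

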no events. We stratified the patients as being high risk for cardiac events if they had history of IHD, peripheral artery disease (PAD), or underwent a PAD-related operation. We ultimately collected information on 171,357 patients who underwent the target operations and were included in our analysis.

FIGURE 2. Probability of the Composite Endpoint at Various Levels of the Postoperative Nadir Hb – Multicenter data

Similarly to the single institutional analysis, a strong association was seen between increasing values of nadir postoperative Hb and freedom from the composite endpoint (OR: 0.566, 95% CI: 0.561 to 0.57, Figure 2). From the initial patient pool, 38,153 patients were at high risk for cardiac events and dropped their nadir postoperative Hemoglobin in the early postoperative period below 10 gm/dl, conditions that would make them eligible for the proposed trial. In this high cardiac risk patient population, the composite outcome occurred in almost 30% of patients with nadir Hb between 6-9 gm/dl (a subset that will represent the restrictive transfusion arm in the proposed study) and in 15% of patients with nadir Hb between 9-10 gm/dl (a subset that will represent the liberal transfusion arm in the proposed trial). Event rates for the composite and individual endpoints are summarized in TABLE 2 below:

TABLE 2. Composite Event Rates and Individual Event Rates among Veterans at High Cardiac Risks after a Surgical Procedure

Nadir Hb	Composite Endpoint	Death	MI	ARF	Coronary Revascularization
6-9 gm/dl	29.5%	15.3%	11.0 %	11.1%	0.4%
9-10 gm/dl	15.0%	6.9%	6.2%	4.1%	0.3%

III. SIGNIFICANCE AND RELEVANCE TO VETERANS

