In order to estimate 90 day composite endpoint rate (defined in Section V) after surgical interventions in the VA population, we conducted an analysis of Vascular and General Surgery operations identical to those targeted in the proposed trial as described in pages 5-7. Data of 171,357 VA patients who underwent these vascular or general procedures and had available nadir Hb level from the Corporate Data Warehouse (CDW) database was used for this analysis. We anticipate in the proposed trial the nadir Hb in the restrictive transfusion group to range between 6-9 gm/dl (transfusion trigger Hb < 7 gm/dl). Our database review revealed that 29.8% out of 25,343 patients who were at high cardiac risk and had nadir postoperative Hb at this range developed the composite endpoint of death, MI, acute renal failure, or coronary revascularization within 90 days from the index operation. The breakdown of event rates for the individual components of the composite endpoint is shown in Table 2 . Based on the analysis, a baseline event rate of 30% for the composite endpoint is expected in the restrictive group.

B. Sample Size Calculation and Power Analysis

The sample size estimation and power analysis are based on the hypothesis testing of the primary composite endpoint, which is the most important measure proposed in the study. According to the analysis of event rates outlined in the previous section, we assume that 30% rate for the primary endpoint can be anticipated in the restrictive transfusion group. We also assume a 25% reduction or 22.5% event rate in the liberal group. The sample size for the study is estimated based on a superiority trial design. To detect the expected 7.5 percentage point difference or 25% reduction, a sample size of 1444 will be required at 90% power, 5% type-I error rate and with a two-sided test (TABLE 3). Assuming 5% dropout rate, then 1520 participants (or 760/group) will be needed to achieve the desired testing power.

TABLE 3 Sample Size Estimation and Power Analysis

90 Day Composite Endpoint (%)				Power (%)			
Liberal	Restrictive	Difference	Percent Difference	75	80	85	90
17.50	25.00	7.50	30.0	826	932	1066	1248
18.75	25.00	6.25	25.0	1214	1372	1570	1836
20.00	25.00	5.00	20.0	1936	2188	2502	2928
21.00	30.00	9.00	30.0	650	734	840	982
22.50	30.00	7.50	25.0	954	1080	1234	1444
24.00	30.00	6.00	20.0	1520	1718	1964	2298
24.50	35.00	10.50	30.0	526	594	678	794

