26.25	35.00	8.75	25.0	770	870	994	1164
28.00	35.00	7.00	20.0	1222	1382	1580	1848

C. Duration of Study and Number of Participating Sites

To calculate the expected study duration and resources, we assume that the recruitment rate will be half of what we anticipate. Under this assumption, various scenarios were examined in order to identify an optimal combination between the number of sites, the study duration (which includes recruitment period and follow-up period) and the estimated budget. By conducting the study with 15 sites and 3 participants/month/site rate of recruitment, the recruitment period was found to be approximately four years. This will be followed by three months of active follow-up and 9 months of passive follow up for the last subject randomized into the study. Thus, the study duration including start-up, will be five years.

D. Feasibility Phase

In order to confirm the hypothesized control proportion for the primary outcome, to determine the feasibility of recruiting average 3 participants per site per month, and to assess other operational aspects of the study, a feasibility phase has been built into this study. The planned duration of the feasibility phase of the study is one year and will include 3 NODES sites (Houston, Minneapolis, and Dallas VA Medical Centers) and five additional sites with existing research infrastructure and high expected recruitment rates (Cleveland, Buffalo, Tampa, Gainesville, and Little Rock VA Medical Centers).

During the feasibility phase, several site start-up activities and operational aspects of the study will be examined. These activities will include the hiring of site personnel (including classification of position descriptions, position announcements and recruitment), the methods by which site staff are trained on data collection and management activities, the practicality of consent, randomization and attrition (drop-out) rates. The lessons learned during this phase will be implemented during activation of the remaining 7 participating sites.

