5.4. Analysis Populations

Intent-to-Treat (ITT) – This population is defined as the population of participants (except non-Veterans and previous participants of this trial) who will be randomized to either of the transfusion strategy groups – Liberal or Restrictive. The participants will be categorized (in terms of their transfusion strategy assignment) based on their initial randomized group and will be included in analyses irrespective of their status – completer or drop out of the study before completion. The testing power for the primary endpoint is estimated as 90% in this population.

Modified Intent-to-Treat (mITT) – This population is defined as a subset of the ITT population that excludes randomized participants in a justified way, i.e., participants who are found to be ineligible (violating inclusion/exclusion criteria) or participating in more than one simultaneous intervention trial.

No-Recent-Transfusion – This population is defined as a subset of the ITT population excluding the participants who will receive transfusions within 30 days prior to or during the index operation, or after the index operation but before randomization.

Completers – This population includes all ITT participants who will complete all protocol-required lab and EKG assessments, hemoglobin monitoring and transfusion records in the hospital stay or until death, as well as completing assessments of the 5 individual components of the primary endpoint at 30 day and 90-day follow-up or until death.

Per Protocol – This population includes all ITT participants who will adhere to transfusion protocol in their assigned intervention groups.

Safety – This population includes all participants (except non-Veterans and previous participants of this trial) who will be randomized to either of the transfusion strategy groups – Liberal or Restrictive.

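### The 30% restrictive-arm rate, and so the unqualified 90% power, is taken from the nadir Hb 6-9 subset, although everyone with Hb below 10 is randomised; at the roughly 25% of the whole eligible pool, 1444 patients give about 82%

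*Protocol*

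**What the plan says.** Protocol XVI.A derives the control rate from the VA data warehouse. It gives the reason for choosing the subset: "We anticipate in the proposed trial the nadir Hb in the restrictive transfusion group to range between 6-9 gm/dl". The rate in that subset was "29.8% out of 25,343 patients who were at high cardiac risk and had nadir postoperative Hb at this range developed the composite endpoint", so "a baseline event rate of 30% for the composite endpoint is expected in the restrictive group". SAP 4.5 repeats this.

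Protocol XVI.B adds the effect, "We also assume a 25% reduction or 22.5% event rate in the liberal group", and concludes that "a sample size of 1444 will be required at 90% power, 5% type-I error rate and with a two-sided test". With 5% dropout this becomes 1520, or 760 per arm. Protocol XVI.E.1 and SAP 5.4 then state for the ITT population, without a condition: "The testing power for the primary endpoint is estimated as 90% in this population".

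Protocol II(c) describes the larger pool from the same database: "38,153 patients were at high risk for cardiac events and dropped their nadir postoperative Hemoglobin in the early postoperative period below 10 gm/dl". It calls these patients eligible for the trial. Its Table 2 gives composite rates of 29.5% for nadir 6-9 and 15.0% for nadir 9-10, and the text lets the first stratum stand for the restrictive arm and the second for the liberal arm.

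Protocol VI randomises once a postoperative Hb below 10 is confirmed. Protocol X requires this within 24 hours of the first such value. Protocol XVI.D gives the feasibility phase this purpose, among others: "In order to confirm the hypothesized control proportion for the primary outcome".

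**The concern.** At randomisation the eventual nadir is unknown. A patient whose Hb would settle at 9.4 is as likely to be assigned to the restrictive arm as to the liberal arm. The restrictive arm is therefore a random half of everyone with Hb below 10, not the group whose nadir turns out to be 6-9. A nadir seen after randomisation cannot define the control rate of a randomised arm, yet the plan gives the whole arm the higher-risk stratum's rate and leaves the lower-risk third of its own eligible pool out.

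With a fixed relative reduction, a lower control rate means a smaller absolute difference and less power. At 82% power the chance of missing the design effect is 18%, against the 10% that the plan states. This matters because Protocol III says that a finding that the restrictive strategy is safe would support it in practically every patient population.

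**Working it through.** **1. The plan's own figure.** Two-sided alpha 0.05, equal arms, pooled variance, no continuity correction:

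n per arm = [1.960·√(2p̄(1−p̄)) + 1.282·√(p₁(1−p₁)+p₂(1−p₂))]² / (p₁−p₂)²

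With p₁ = 0.30, p₂ = 0.225 and p̄ = 0.2625, this is [1.960 × 0.6222 + 1.282 × 0.6200]² / 0.075² = 721.2, so 722 per arm and 1444 in total. 1444/0.95 = 1520. Power at 722 per arm is 90.0%. All three stated figures reproduce.

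**2. The rate in the whole eligible pool.** Inputs: 38,153 eligible (Protocol II(c)); 25,343 with nadir 6-9 at 29.8% (XVI.A); 15.0% for nadir 9-10 (Table 2).

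- Remainder: 38,153 − 25,343 = 12,810, or 33.6%.
- Pool rate: (25,343 × 0.298 + 12,810 × 0.150) / 38,153 = (7,552 + 1,922) / 38,153 = 24.8%. With Table 2's 29.5% in place of 29.8% it is 24.6%.

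This assumes that the whole remainder had nadir 9-10, since nadirs below 6 are not reported separately. If 2-5% of the pool were below 6 with event rates of 30-60% (assumed), the pool rate would be 25.1-27.1% and power about 82-86%.

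**3. Power at that rate.** Keeping the 25% relative reduction and 722 per arm, at 25% vs 18.75%:

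z = [0.0625·√722 − 1.960 × 0.5846] / 0.5830 = 0.915, so power is 82.0%.

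The plan's Table 3 agrees: its 25% vs 18.75% row needs 1372 for 80%, 1570 for 85% and 1836 for 90%.

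**4. Allowing for a shift in nadir.** Under a trigger of 7, some patients in the 9-10 group may fall lower. If a fraction s of them took on the 6-9 rate (assumption), the rate is [(25,343 + s·12,810) × 0.298 + (1−s)·12,810 × 0.150] / 38,153.

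| s | Restrictive rate | Power at 1444 |
|---|---|---|
| 0 | 24.8% | 82% |
| 0.25 | 26.1% | 84% |
| 0.50 | 27.3% | 86% |
| 0.75 | 28.6% | 88% |
| 1 | 29.8% | 90% |

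On these data alone, 90% needs essentially the whole group to take on the higher risk.

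**5. Power by round planning value.** At 1444 evaluable: 82.0% at 25%, 83.9% at 26%, 85.6% at 27%, 87.2% at 28%, 88.7% at 29%, 90.0% at 30%. If all 1520 contributed outcomes: 83.9% at 25% and 91.4% at 30%.

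**6. The feasibility phase.** Protocol XVI.D expects 288 participants in year one, so at most 288/2 = 144 controls. The 95% half-width at a rate of 30% is 1.96·√(0.30 × 0.70/144) = 7.5 points (7.1 at 25%). That cannot separate 25% from 30%. XVI.D links recruitment experience to a revised projection, but links no action to the observed event rate.

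**The case against.** Several points against this are sound.

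- **The plan's calculation is right for its inputs, and XVI.A states the assumption openly.** That stands. A reader might infer an arithmetic error; there is none.
- **24.8% is a low-end value for the restrictive arm.** The data come from 2000-2014, and Protocol I describes transfusion below 10 as the historical standard. Some nadirs of 9-10 may have stayed there because patients were transfused. This stands, and it is why step 4 shows a range. Similarly, if 24.8% is read as the average of the two arms, the restrictive rate is 2 × 24.8/1.75 = 28.4% and power about 88%.
- **The database undercounts the trial endpoint.** Protocol II(c) found no strokes by code, against about 1% in single-institution data. It required a troponin of at least 1 ng/ml from clinically ordered tests, and it could not apply urine-output criteria. The trial schedules troponin, uses the Third Universal Definition and applies urine output in ICU. All of this could raise the trial's rate; about 5 points on 24.8% would restore 90%.
- **The time origin differs.** The database counts from operation. That includes events before randomisation, but the window also closes up to 15 days earlier. The net effect is not given.
- **An absolute difference of 7.5 points at 25% (25% vs 17.5%) would give 93.7% power.** True, but that is a 30% relative reduction, larger than the plan assumes.
- **Table 3 prints the 25% row, Protocol XVI.E promises a 95% interval if the null is not rejected, and the DMC receives conditional power.** These limit the harm. They do not tell a reader that the eligible pool points to the 25% row, and the underlined row and the ITT statement both present 90% unqualified.

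**Conclusion.** The point holds as a fault in a planning input. The 30% belongs to about two thirds of the eligible pool (66.4%) and is applied to an arm drawn from all of it. With no nadirs below 6, no shift in nadir under the trigger of 7 and a 25% relative reduction, the rate is about 25% and power at 1444 about 82%; with a shift of one half to three quarters of the 9-10 group it is about 86-88%.

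A reader might go further and conclude that the trial cannot have 90% power, or that its true power is 82% or some fixed range below 90%. The documents do not support that. Undercounting of stroke, MI and renal failure could close the gap, and neither that nor the effect of the different time origin is quantified. What can be said is that 90% depends on a restrictive rate near 30%, that the cited subset does not establish that rate for the randomised arm, and that the feasibility phase is too small to settle it.

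**What to change.** 1. In Protocol XVI.A, XVI.B and XVI.E.1 and SAP 4.5 and 5.4, replace the unqualified 90% with power conditional on the restrictive rate, for a 25% relative reduction at 1444 evaluable: about 82% at 25%, 86% at 27%, 87% at 28% and 90% at 30%.
2. State beside it that 30% assumes either that essentially all restrictive-arm patients carry the risk seen at nadir 6-9, or that database undercounting makes up the difference.
3. In Protocol XVI.D, drop the aim of confirming the control proportion.
4. At the existing 25% and 50% looks, compare the blinded pooled event rate with the planning values. Under a 25% reduction the pooled rate is 0.875 times the restrictive rate: 26.3% if that rate is 30%, 21.9% if it is 25%. With 760 participants (half of 1520) the 95% half-width at 26.25% is 1.96·√(0.2625 × 0.7375/760) = 3.1 points, enough to be informative. A low pooled rate could also reflect a larger effect, so it should be reported as a check on the assumptions, not as an estimate of the control rate.

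The cost is a less favourable stated power. No patients are added, and neither the test nor the conduct of the trial changes.
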